8.12.2. Dose Modifications and Management Associated with Nivolumab and/or Ipilimumab

Dose delay criteria apply for all drug-related adverse events (regardless of whether the event is attributed to nivolumab or ipilimumab or both). Delay administration of both nivolumab and ipilimumab if any of the delay criteria are met. Delay nivolumab and ipilimumab dosing for any adverse event, laboratory abnormality, or intercurrent illness which, in the judgment of the Investigator, warrants delaying the dose of study medication.

For subjects who require the delay of nivolumab and ipilimumab, re-evaluate weekly, or more frequently, if clinically indicated and resume dosing when criteria to resume treatment are met. Continue tumor assessments per protocol even if dosing is delayed.

If discontinuation criteria are met for ipilimumab but not for nivolumab, treatment with nivolumab may continue; if nivolumab is discontinued, however, ipilimumab will not continue as monotherapy.

If a subject meets criteria for discontinuation of nivolumab/ipilimumab and Investigator is unable to determine whether the event is related to both or one study drug, the participant must discontinue both nivolumab and ipilimumab. Subjects may continue receiving ivosidenib. If subject permanently discontinues treatment from all three drugs, EOT and Safety Follow-up Visits will be completed, as well as PFS follow-up (if disease has not progressed) and survival follow-up visits.

Subjects may resume treatment with nivolumab/ipilimumab if they have completed AE management (*i.e.* corticosteroid taper) or are on ≤ 10 mg prednisone or equivalent, and meet the requirements per [Appendix 8](#) and [Appendix 9](#).

Prior to re-initiating treatment in a participant with a dosing delay lasting > 8 weeks for Q3 week treatment and 10 weeks for Q4 week treatment, the Medical Monitor (or designee) must be consulted.

8.12.3. Dose Modification for Ivosidenib, Nivolumab and Ipilimumab

When study interventions are administered in combination, attribution of an AE to a single component is likely to be difficult. When an AE cannot be clearly attributed to any one or combination of drugs, the most stringent criteria for dose modification (based on Dose modification for ivosidenib and ipilimumab/nivolumab - [Table \(8.12.1\) 1](#) and [Appendix 8](#)) must be used for all three drugs.

Dose delay: When study interventions are administered in combination, if the AE is considered immune-related, both nivolumab and ipilimumab interventions should be held according to recommended dose modifications ([Appendix 8](#)). QTc prolongation and other Grade3 or higher adverse events that are possibly related to ivosidenib should be managed according to dose modification recommendations in [Table \(8.12.1\) 1](#).

Re-starting Study Interventions: Subjects may not have any dose modifications (no change in dose or schedule) of nivolumab and/or ipilimumab in this study. At the 250 mg QD dose level, no dose re-escalation is allowed for ivosidenib. If the toxicity does not resolve or the criteria for resuming treatment are not met, the subject must be discontinued from all study interventions. If the toxicities do resolve and conditions are aligned with what is defined in [Appendix 8](#) and [Table \(8.12.1\) 1](#) ivosidenib, nivolumab and/or ipilimumab may be restarted at the discretion of the Investigator.

8.12.4. Treatment of Related Infusion Reactions Associated with Nivolumab and Ipilimumab

Since nivolumab and ipilimumab contain only human immunoglobulin protein sequences, they are unlikely to be immunogenic and induce infusion or hypersensitivity reactions. However, if such a reaction were to occur, it might manifest with fever, chills, rigors, headache, rash, pruritus, arthralgias, hypotension, hypertension, bronchospasm, or other allergic-like reactions. Report all Grade 3 or 4 infusion reactions within 24 hours as an SAE if it meets the criteria.

Treatment recommendations are provided below based on NCI CTCAE v5.0 grading definitions and may be modified based on local treatment standards and guidelines, as appropriate:

For Grade 1 symptoms (mild reaction; infusion interruption not indicated; intervention not indicated):

- Remain at bedside and monitor participant until recovery from symptoms. The following prophylactic premedications are recommended for future infusions: diphenhydramine 50 mg (or equivalent) and/or acetaminophen/paracetamol 325 to 1,000 mg at least 30 minutes before additional nivolumab administrations.

For Grade 2 symptoms (therapy or infusion interruption indicated but responds promptly to symptomatic treatment (e.g., antihistamines, non-steroidal anti-inflammatory drugs, narcotics, IV fluids); prophylactic medications indicated for ≤ 24 hours):

- Stop the study drug infusion, begin an IV infusion of normal saline, and treat the participant with diphenhydramine 50 mg IV (or equivalent) and/or acetaminophen/paracetamol 325 to 1,000 mg; remain at bedside and monitor participant until resolution of symptoms. Corticosteroid and/or bronchodilator therapy may also be administered as appropriate. If the infusion is interrupted, then restart the infusion at 50% of the original infusion rate when symptoms resolve; if no further complications ensue after 30 minutes, the rate may be increased to 100% of the original infusion rate. Monitor participant closely. If symptoms recur, then no further study medication will be administered at that visit.
- For future infusions, the following prophylactic premedications are recommended: diphenhydramine 50 mg (or equivalent) and/or acetaminophen/paracetamol 325 to 1,000 mg administered at least 30 minutes before nivolumab and/or ipilimumab infusions. If necessary, corticosteroids (up to 25 mg of hydrocortisone or equivalent) may be used.

For Grade 3 or 4 symptoms (severe reaction, Grade 3: prolonged [e.g., not rapidly responsive to symptomatic medication and/or brief interruption of infusion]; recurrence of symptoms following initial improvement; hospitalization indicated for clinical sequelae. Grade 4: life-threatening consequences; urgent intervention indicated):

- Immediately discontinue infusion of study drug. Begin an IV infusion of normal saline and treat the participant as follows: Recommend bronchodilators, epinephrine 0.2 to 1 mg of a 1:1,000 solution for subcutaneous administration or 0.1 to 0.25 mg of a 1:10,000 solution injected slowly for IV administration, and/or diphenhydramine 50 mg IV with methylprednisolone 100 mg IV (or equivalent), as needed. Monitor participant until the Investigator judges that the symptoms will not recur. Study drug will be permanently discontinued. Follow institutional guidelines for the treatment of anaphylaxis. Remain at bedside and monitor participant until recovery of the symptoms.

In case of late-occurring hypersensitivity symptoms (e.g., appearance of a localized or generalized pruritus within 1 week after treatment), symptomatic treatment may be given (e.g., oral antihistamine or corticosteroids).

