	Suspected Stevens-Johnson syndrome (SJS), toxic epidermal necrolysis (TEN) or drug reaction with eosinophilia and systemic symptoms (DRESS)	Delay dose	Dosing may resume if SJS, TEN, or DRESS is ruled out and rash reduces to is ≤ 10% body surface area
	Grade 4 rash or confirmed SJS, TEN, or DRESS	Permanently discontinue	
Neurological			
Guillain-Barre Syndrome (GBS)	Any grade	Permanently discontinue	
Myasthenia Gravis (MG)	Any grade	Permanently discontinue	
Encephalitis	Any grade encephalitis	Delay dose	After workup for differential diagnosis, (i.e., infection, tumor-related), if encephalitis is not drug related, then dosing may resume when AE resolves
	Any grade drug-related encephalitis	Permanently discontinue	
Myelitis	Any grade myelitis	Delay dose	After workup for differential diagnosis, (i.e., infection, tumor-related), if myelitis is not drug related, then dosing may resume when AE resolves
	Any grade drug-related myelitis	Permanently discontinue	
Neurological (other than GBS, MG, encephalitis, or myelitis)	Grade 2	Delay dose	Dosing may resume when AE resolves to baseline
	Grade 3 or 4	Permanently discontinue	
Myocarditis			
Myocarditis	Symptoms induced from mild to moderate activity or exertion	Delay dose	Dosing may resume after myocarditis has resolved

Drug-Related Adverse Event (AE) per CTCAE V5	Severity	Action Taken	Clarifications, Exceptions, and Resume Criteria
	Severe or life-threatening, with symptoms at rest or with minimal activity or exertion, and/or where intervention indicated.	Permanently discontinue	
Other Clinical AE			
Pancreatitis: Amylase or Lipase increased	Grade 3 with symptoms	Delay dose	Note: Grade 3 increased amylase or lipase without signs or symptoms of pancreatitis does not require dose delay. Dosing may resume when subject becomes asymptomatic.
	Grade 4	Permanently discontinue	
Uveitis	Grade 2 uveitis	Delay dose	Dosing may resume if uveitis responds to topical therapy (eye drops) and after uveitis resolves to Grade ≤ 1 or baseline. If subject requires oral steroids for uveitis, then permanently discontinue study drug.
	Grade 3 or 4 uveitis	Permanently discontinue	
Other Drug-Related AE (not listed above)	Grade 2 non-skin AE, except fatigue	Delay dose	Dosing may resume when AE resolves to Grade ≤ 1 or baseline value.
	Grade 3 AE - First occurrence lasting ≤ 7 days	Delay dose	Dosing may resume when AE resolves to Grade ≤ 1 or baseline value.
	Grade 3 AE- First occurrence lasting > 7 days	Permanently discontinue	

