	Recurrence of Grade 3 AE of any duration	Permanently discontinue	
	Grade 4 or Life-threatening adverse reaction	Permanently discontinue	

Drug-Related Adverse Event (AE) per CTCAE V5	Severity	Action Taken	Clarifications, Exceptions, and Resume Criteria
Other Lab Abnormalities			
Other Drug-Related lab abnormality (not listed above)	Grade 3	Delay dose	
Exceptions: No delay required for: Grade 3 lymphopenia
 
Permanent Discontinuation for: Grade 3 thrombocytopenia > 7 days or associated with bleeding.

	Grade 4	Permanently discontinue	
Exceptions: The following events do not require discontinuation of study drug:
 
 • Grade 4 neutropenia \leq 7 days • Grade 4 lymphopenia or leukopenia • Grade 4 isolated electrolyte imbalances/abnormalities that are not associated with clinical sequelae and are responding to supplementation/appropriate management within 72 hours of their onset

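### For a first related Grade 3 infusion reaction lasting 7 days or less, Protocol Section 8.12.4 calls for permanent discontinuation while Appendix 8's residual row permits resumption, with no order of precedence stated

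*Protocol*

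**What the plan says.** - **Protocol Section 8.12.4** (infusion reactions to nivolumab and ipilimumab). The severe category opens "For Grade 3 or 4 symptoms (severe reaction, Grade 3: prolonged" and ends in one action for both grades: "Monitor participant until the Investigator judges that the symptoms will not recur. Study drug will be permanently discontinued". It gives no duration condition and no route back to dosing. The section introduces its contents as treatment recommendations that "may be modified based on local treatment standards and guidelines, as appropriate".
- **Protocol Appendix 8** (dosing criteria for nivolumab and ipilimumab). It has no row for infusion or hypersensitivity reactions. Its residual row is "Other Drug-Related AE (not listed above"). There, "Grade 3 AE - First occurrence lasting ≤ 7 days" leads to a dose delay, and "Dosing may resume when AE resolves to Grade ≤ 1 or baseline value". A longer first Grade 3 event, a recurrent Grade 3 event, and "Grade 4 or Life-threatening adverse reaction" all lead to permanent discontinuation.
- **Protocol Section 8.12.2** applies the delay criteria to every drug-related adverse event and ties resumption to Appendices 8 and 9.
- **Protocol Section 8.12.3** says that once toxicities resolve and the conditions in Appendix 8 and Table (8.12.1) 1 are met, the drugs "may be restarted at the discretion of the Investigator".
- **Protocol Section 4.1.4.3** (DLT management) makes withdrawal from all three drugs the default. It allows resumption if the Investigator sees clinical benefit and a manageable event and the Sponsor approves, and it expressly provides for restarting nivolumab and/or ipilimumab.

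**The concern.** The same short, first Grade 3 infusion reaction can be read under two places that give different instructions. Neither refers to the other, and no order of precedence is stated. A site that treats Appendix 8 as the dosing rule and Section 8.12.4 as bedside care could restart an antibody after a reaction for which Section 8.12.4 calls for permanent discontinuation. What is at stake is mainly participant safety: whether someone is re-exposed after a severe reaction would depend on which page the site consulted. It also bears on conduct, because Section 14.2 of the protocol permits no deviations, yet a restart here would comply with one text and breach another.

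**Working it through.** No arithmetic applies. The check sets the texts side by side for a treatment-related infusion reaction of Grade 3 or 4.

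| Reaction | Section 8.12.4 | Appendix 8, residual row | Same action? |
|---|---|---|---|
| First Grade 3, 7 days or less | Permanent discontinuation | Delay; may resume | No |
| First Grade 3, more than 7 days | Permanent discontinuation | Permanent discontinuation | Yes |
| Recurrent Grade 3, any duration | Permanent discontinuation | Permanent discontinuation | Yes |
| Grade 4 | Permanent discontinuation | Permanent discontinuation | Yes |

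**Could the first row of the table be empty?** Section 8.12.4 describes Grade 3 as prolonged, but explains this by poor response to symptomatic medication or to a brief interruption of the infusion. It sets no minimum in days, so a Grade 3 reaction can last 7 days or less.

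**Does another rule break the tie?** Three candidates were checked.

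1. Section 8.12.2 covers all drug-related events and makes no exception for infusion reactions, so it leads to Appendix 8.
2. Section 8.12.3 has a most-stringent-criteria rule. It applies only when attribution is unclear, and it names Table (8.12.1) 1 and Appendix 8, not Section 8.12.4.
3. Section 8.12.4 does not say that it overrides Appendix 8, and its opening allows local modification.

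**What happens in the DLT window?** Under Section 4.1.4.2, a related Grade 3 or higher event that is not immune-related is a DLT unless listed as an exclusion. Infusion reactions are not listed. In the first 42 days of the Safety Lead-in such a reaction would therefore ordinarily be a DLT, and Section 4.1.4.3 would apply as a third text. Its resumption route, conditional on Sponsor approval, is not limited by grade or duration, so it also needs aligning with Section 8.12.4.

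**The case against.** The strongest reply is that a specific rule governs a general one. Section 8.12.4 is written for infusion reactions and is firm on this point. Appendix 8 is reached only through a residual row that never mentions them, and both that row and Section 8.12.3 merely permit a restart. A site that follows Section 8.12.4 breaches nothing in Appendix 8. This stands to the extent that the texts do not require opposite actions, as a reader might infer: one directs discontinuation and the other permits resumption. It does not remove the inconsistency. The protocol states no such hierarchy, Section 8.12.4 softens its own status by allowing local modification, and the site that restarts is the one left in contradiction.

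A second reply is that Section 8.12.2 already settles which drug is meant. Ipilimumab does not continue if nivolumab is stopped, nivolumab may continue if only ipilimumab meets the criteria, and both stop if the event cannot be assigned between them. This largely answers the question once attribution is made, but Section 8.12.4 does not refer to it.

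A third reply is that Section 4.1.4.3 limits uncontrolled restarts in the DLT window, because withdrawal is the default and Sponsor approval is needed. That is fair, and it reduces the room for sites to differ during Cycles 1 and 2. It does not cover later cycles.

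**Conclusion.** The protocol gives conflicting instructions for one defined case: a first, treatment-related Grade 3 infusion reaction lasting 7 days or less. This rests on reading the Appendix 8 residual row literally, which nothing in the protocol rules out. For the other Grade 3 and Grade 4 cases, Section 8.12.4 and Appendix 8 agree.

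Three stronger inferences are not supported:

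- **DLT evaluability.** A reader might think that stopping the antibodies early costs a participant DLT evaluability, which without a DLT requires two doses of each. On the ordinary reading, a related Grade 3 reaction in the window is itself a DLT, so the participant is evaluable however many doses follow.
- **Frequency.** A reader might assume that most severe infusion reactions resolve within days and so usually meet the resumption row. The documents give neither an incidence nor a duration for these reactions.
- **Statistical size.** With 7 enrolled, one participant is 1/7 = 14.3 percentage points of any row, including discontinuations. That is the weight of any single participant, not a measure of this issue. No planned figure depends on the conflict.

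Severity is low. SAP Sections 1 and 5 state that enrollment stopped at 7, that the study did not proceed to the Expansion phase, and that an early termination letter was issued on 21 August 2024. Some reach could remain, because Protocol Section 4.3.1 lets benefiting participants stay on treatment if the study ends for reasons other than safety. The documents do not say whether anyone did.

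**What to change.** Reconcile Section 8.12.4, Appendix 8 and Section 4.1.4.3 so that one instruction applies to a Grade 3 infusion reaction. Either add an infusion or hypersensitivity reaction row to Appendix 8, or exclude these reactions from its residual row with a pointer to Section 8.12.4. Add a matching cross-reference in Section 4.1.4.3. In Section 8.12.4, state whether the discontinuation instruction is among the contents that may be modified locally, and which infused drug or drugs it covers, with a reference to Section 8.12.2. Which action applies is for the sponsor's clinical team to decide.

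The cost is one row or exclusion in Appendix 8, one cross-reference in Section 4.1.4.3 and a clarifying sentence in Section 8.12.4. No analysis in the SAP changes.

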8.12.5. Biliary Tract Obstruction During Treatment

In the event of the development of obstructive jaundice due to biliary tract obstruction, the appropriate measures will be taken to diagnose and relieve the obstruction. Study treatment interruption is not required but will be permitted at the discretion of the Investigator.

9. OTHER ASSESSMENTS NOT SPECIFICALLY RELATED TO EFFICACY OR SAFETY

9.1. Assessments Related to Inclusion Criteria

All Screening procedures must be performed within 28 days prior to first dose for subjects in the Safety Lead-in or the Expansion phase. A legally authorized representative may consent on behalf of a subject who is otherwise unable to provide informed consent if acceptable to and approved by the site's IRB/IEC.

Inclusion and Exclusion Criteria

Inclusion and exclusion criteria (Section 5.1 and Section 5.2, respectively) will be reviewed for each potential subject and documented in the subject medical record and eCRF.

Demographic Data, and Medical, Surgical, and Disease History

Subject demographic data, including sex, year of birth, age, race, and ethnicity, will be obtained during Screening and according to applicable local regulations.

A complete medical, surgical, and disease history, and the date of initial diagnosis of the underlying CCA, will be obtained during Screening. The medical history is to include all relevant prior medical history as well as all current medical conditions.

All medications administered and procedures conducted within 28 days before the first dose of IMP through 30 days after last dose of IMP should be reported in the eCRF.

9.2. Measurement of Drug Concentration

9.2.1. Sample Collection Time Points

Serial or sparse blood samples will be drawn before and after dosing of study treatment in order to determine circulating plasma and tissue concentrations of ivosidenib. The blood samples will also be used for the determination of 2-HG concentrations (see Section 9.3).

Blood samples will be drawn on Day 1 of Cycle 2 (for Safety Lead-in phase) or Day 1 of Cycle 4 (for Expansion phase) at the following time points: pre-dose (within 30 minutes before ivosidenib dose), 2, 3, 4, and 6 hours (\pm 10 minutes) post-dose. Additional blood samples for ivosidenib PK and 2-HG PD assessments will be drawn pre-dose (within 30 minutes before ivosidenib dose) on C1D1, C1D15, C2D1, C3D1, C4D1, C5D1, and Day 1 of every cycle through Cycle 13, and Day 1 of every other cycle thereafter.

Sparse blood samples will also be drawn before and after dosing of study treatment in order to determine circulating serum concentrations of nivolumab and ipilimumab. Specifically, for nivolumab serum concentration assessment, blood samples will be drawn at pre-dose (within 30 minutes before the ivosidenib dose) on C1D1, C2D1, C3D1, and C4D1, followed by pre-dose collection on Day 1 of every 4 cycles up to 2 years, and at end of infusion after first dose of nivolumab on C1D1. For ipilimumab serum concentration assessment, blood samples will be drawn at pre-dose (within 30 minutes before the ivosidenib dose) on C1D1, C2D1, C3D1, and C4D1, and at end of infusion after first dose of ipilimumab on C1D1. Predose samples for all three IMPs may be collected in one blood draw.

If enough material is available, tumor tissue (fresh-frozen) may be used to determine tumor drug concentration of ivosidenib in order to evaluate tumor exposure of ivosidenib on C1D1 and C3D1. Tumor sample collection is detailed in Section 9.3.

9.2.2. Sampling Methods

Blood for assessment of PK parameters of ivosidenib and 2-HG concentrations will be collected and processed according to the laboratory manual. Every effort will be made to collect PK samples at the time points specified. No additional samples will be collected without formal amendment to this protocol. Analysis will be performed at a central laboratory (Specialty Laboratory) using validated bioanalytical methods. A detailed laboratory manual specifying

sample collection, processing, handling, storage, and shipment will be provided to the study sites; retention time for specimens will be specified therein. If a collected plasma sample is inadequate or insufficient for PK analysis, the analysis of PK can be done using samples for biomarker studies.

9.3. Pharmacodynamics Measurements

Samples of blood for measuring the plasma concentrations of 2-HG will be obtained before the first dose of ivosidenib given on C1D1 (within 30 minutes before the ivosidenib dose). Additional PD samples include single pre-dose blood samples that will be collected prior to dosing ivosidenib (within 30 minutes before the ivosidenib dose) on C1D15, C2D1, C3D1, C4D1, C5D1, and Day 1 of every cycle through Cycle 13, and Day 1 of every other cycle thereafter (e.g., Cycles 15, 17, etc.).

Subjects will be requested to have tumor tissue newly collected at Screening for baseline tumor 2-HG measurement and other exploratory biomarker assessment. A post-dose tumor sample will be collected on C3D1 for 2-HG measurement and other exploratory biomarker assessments.

All time points are described in the investigational schedule.

Biopsies can be collected at Screening and on C3D1 from a similar site as screening. At each time point, tumor biopsies must include at a minimum 3 core needle samples (3 to 4 core samples if feasible). If a subject cannot undergo a biopsy at Screening, archived fresh-frozen tumor biopsy, if available, can be used for the measurement of baseline 2-HG.

If a required tumor biopsy (any time point) cannot be performed due to concerns around subject safety, a discussion with the Sponsor is required and biopsy can be omitted.

The tissue obtained by core needle biopsy will be:

- Fixed in 10% normal buffered formalin and later embedded in paraffin to produce slides for biomarker assessments (detailed in Section 9.5).
- Processed as fresh-frozen tissue for assessment of concentrations of 2-HG (using liquid chromatography with tandem mass spectrometry).
- If there is enough material, samples may also be used for determining tumor drug concentrations of ivosidenib or for assessment of other exploratory biomarkers.

Detailed instructions for the collection, handling, processing, storage, and shipment conditions will be outlined in the laboratory manual (or equivalent) for the study and provided to the study sites.

